6.3 STUDY VISIT SCHEDULE

Below is a condensed description of the study visits and the procedures and examinations that will be performed. Please refer to the Schedule of Activities (SoA) table in Section 1.2 for a detailed schedule of procedures/assessments for the Monthly visit schedules. Additional safety assessments not listed in section 8.3 or the flow chart may be performed if considered necessary at the discretion of the PI.

6.3.1 SCREENING – WITHIN 14 DAYS PRIOR TO TREATMENT

Visit 1 – All Subjects

All ophthalmic procedures (including imaging) are to be performed on both eyes:

1. Before any study specific procedures are performed, explain the purpose and nature of the study, and have the patient read, sign, and date the Institutional

Review Board/Independent Ethics Committee (IRB/IEC) - approved Informed Consent Form (ICF). Have the individual obtaining consent from the patient and a witness, if applicable, sign and date the ICF.

2. Obtain a screening number for the subject.
3. Obtain information on demographics, medical/ocular history, and concomitant medications used 90 days prior to enrollment. Include vitamins, and all over-the-counter as well as prescription medications.
4. Screen the patient for inclusion/exclusion criteria.
5. Collect blood (including blood for HCG/FSH/LH, if applicable) and urine for laboratory analysis and forward the samples to the central laboratory.
6. Collect vital signs.
7. Perform BCVA.
8. Perform LL-BCVA.
9. Perform a complete ophthalmic exam including slit-lamp exam of the cornea, iris, anterior chamber, lens (LOCS III if any opacity on the lens noted) and aqueous reaction (cells and flare), dilated fundus exam of the vitreous and retina and IOP measurement.
10. Perform SD-OCT imaging for determination of eligibility by the PI.
11. Perform FAF imaging for determination of eligibility by the PI.
12. Perform NIFR imaging.
13. Perform DCFP for determination of eligibility by the PI.
14. Perform FA for determination of eligibility by the PI.

6.3.2 Visit 2 (Baseline) – All subjects

Unless specified, all ophthalmic procedures (including imaging) are to be performed on the **Study eye only**.

1. Verify that all inclusion/exclusion criteria are met, including the determination of eligibility by the PI.
2. Obtain information on any changes in medical health and/or the use of concomitant medications.
3. Collect vital signs pre- and post-dose. Vital signs will be measured within 1 hour prior to dosing for the pre-dose time point. Post-dose vital signs readings will be performed within 30 minutes after dosing.
4. Perform BCVA.
5. Perform LL-BCVA.
6. Perform a complete ophthalmic exam including slit-lamp exam of the cornea, iris, anterior chamber, lens (LOCS III if any opacity on the lens noted) and aqueous reaction (cells and flare), dilated fundus exam of the vitreous and retina and IOP measurement.
7. Perform the IVT injection of fludrocortisone acetate.
8. Monitor the study eye within 15 minutes' post injection.
9. Monitor for adverse events.

6.3.3 Visit 3 (Day 1) – All Subjects. Post-initial treatment examination

Unless specified, all ophthalmic procedures (including imaging) are to be performed on the **study eye only**.

1. Obtain information on any changes in medical health and/or the use of concomitant medications.
2. Collect vital signs.
3. Perform BCVA.
4. Perform LL-BCVA.

5. Perform a complete ophthalmic exam including slit-lamp exam of the cornea, iris, anterior chamber, lens (LOCS III if any opacity on the lens noted) and aqueous reaction (cells and flare), dilated fundus exam of the vitreous and retina and IOP measurement.
6. Monitor for adverse events

6.3.4 Follow-up Visits – Day 7, 14, 28, 60, 90

Unless specified, all ophthalmic procedures (including imaging) are to be performed on the **study eye only**. The following procedures will be performed at all follow-up visits:

1. Obtain information on any changes in medical health and/or the use of concomitant medications.
2. Collect vital signs.
3. Collect blood for PK analysis (days 7, 28 and 90 only).
4. Perform a complete ophthalmic exam including slit-lamp exam of the cornea, iris, anterior chamber, lens (LOCS III if any opacity on the lens noted) and aqueous reaction (cells and flare), dilated fundus exam of the vitreous and retina and IOP measurement.
5. Monitor for adverse events

6.3.5 Termination Visit (or Early Termination) – Day 150

All ophthalmic procedures are to be performed on BOTH EYES.

1. Obtain information on any changes in medical health and/or the use of concomitant medications.
2. Collect blood and urine for laboratory analysis and forward the samples to the central laboratory.
3. Collect blood for PK analysis.
4. Collect vital signs.
5. Perform urine pregnancy test. -WOCBP only.
6. Perform BCVA.

7. Perform a complete ophthalmic exam including slit-lamp exam of the cornea, iris, anterior chamber, lens (LOCS III if any opacity on the lens noted) and aqueous reaction (cells and flare), dilated fundus exam of the vitreous and retina and IOP measurement.
7. Perform SD-OCT imaging.
8. Perform FAF imaging.
9. Perform NIFR imaging.
10. Perform DCFP.
11. Perform FA imaging.
12. Monitor for adverse events

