1.2 SCHEDULE OF ACTIVITIES (SOA)

	Screening Day -14 to -1	Baseline Visit 1, Day 0	Study Visit 2 Day 1 +/-1 day	Study Visit 3 Day 7 +/- 1 day	Study Visit 4 Day 14 +/-1 day	Study Visit 5 Day 28 +/-1 day	Study Visit 6 Day 60 +/-1 day	Study Visit 7 Day 90 +/-1 day	Final Study Visit 8 Day 150 +/-1 day
Procedures									
Informed consent	X								
Demographics	X								
Medical history	X								
Concomitant Medications	X	X	X	X	X	X	X	X	X
Adverse event review			X	X	X	X	X	X	X
Administer study intervention		X							
Physical exam	X	X			X			X	X
Vital signs	X	X	X	X	X	X	X	X	X
Best corrected visual acuity (BCVA)	X	X	X	X	X	X	X	X	X
Height and Weight	X						X		X
Visual Function Questionnaire (VFQ-25)		X							X
Goldmann Intraocular Pressure (IOP)	X	X	X	X	X	X	X	X	X
Slit lamp biomicroscopy, incl. lens grading	X	X	X	X	X	X	X	X	X
Dilated ophthalmoscopy	X	X	X	X	X	X	X	X	X
SD-OCT	X	X	X	X	X	X	X	X	X
FAF and NIFR	X	X	X	X	X	X	X	X	X
Colour Fundus Photography	X						X		X
Fluorescein angiogram	X								X
Haematology & Urinalysis	X	X		X		X			X
Serum chemistry ^a	X	X		X		X			X
Urine Pregnancy test ^b	X								X
Pharmacokinetic sampling		X		X		X			X
Complete Case Report Forms (CRFs)	X	X	X	X	X	X	X	X	X
a: Albumin, alkaline phosphatase, total bilirubin, bicarbonate, BUN, calcium, chloride, creatinine, glucose, LDH, phosphorus, potassium, total protein, AST, ALT, sodium. b: Serum pregnancy test (women of childbearing potential).									

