3.2.2 SECONDARY ENDPOINTS

- The change in square root geographic atrophy (GA) lesion size from baseline to Month 6 as measured by FAF.
- Change in best corrected visual acuity (BCVA).
- Change in low luminance best corrected visual acuity (LL-BCVA).
- Relationship between GA lesion size changes and changes in BCVA.
- Change in vital signs.

- Increase in intraocular pressure (IOP).

Pharmacokinetic (PK) parameters

- Exposure after single dose Fludrocortisone acetate IVT injections.
- Serum maximum observed concentration.
- Time to maximum measured concentration
- Terminal elimination half-life.

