7.7 OCULAR IMAGING

The following ocular images will be obtained as outlined in the visit schedule in Section 6.3. Also see Study Flow Charts in Section 1.2.

- Digital Color Fundus Photographs
- Fluorescein angiography
- Spectral Domain Optical coherence tomography
- Fundus Autofluorescence
- Infrared reflectance imaging. Only done at selected clinical sites with Heidelberg Spectralis® system.
-

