8.1 POPULATION FOR ANALYSIS

- Safety Analysis:

All subjects who received at least one dose of treatment will be included in the evaluation of safety of FCA.

- Efficacy Endpoint(s):

The efficacy analysis will be based on an intention-to-treat population (ITT), which is defined as all subjects who received the single dose of treatment and have at least one visit at or after month 2. Month 2 is the first visit on treatment at which lesion area is measured. Per protocol (PP) efficacy analyses will include all randomized subjects who return for Day 150 of follow up.

Safety is the main analysis population for safety endpoints, and ITT is the main analysis population for efficacy endpoints. The assignment of participants to each analysis population will be based on the review of data after the completion of all data collection, monitoring by the clinical research associate and first round of query resolution by data management and prior to database lock.

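### Section 6.3 and the Schedule of Activities give conflicting assessment schedules, LL-BCVA has no explicit visit after Day 1, and the lesion-timing statement behind the Section 8.1 ITT population fits neither schedule

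*Protocol*

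**What the plan says.** Five parts of the protocol bear on what is measured and when.

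- **Section 1.2 (SoA).** The row "Best corrected visual acuity (BCVA" is marked in all nine columns, as are SD-OCT and FAF. The row "Haematology & Urinalysis" and the serum chemistry row are marked at screening and Days 0, 7, 28 and 150. "Pharmacokinetic sampling" is marked at Days 0, 7, 28 and 150. There is no row for LL-BCVA.
- **Section 6.3.** It describes itself as condensed and refers to the SoA for detail. Section 6.3.4 then says "The following procedures will be performed at all follow-up visits" and numbers five items: health and medication changes, vital signs, PK, the complete ophthalmic exam and adverse events. Its PK item reads "Collect blood for PK analysis (days 7, 28 and 90 only". Section 6.3.2 (Day 0) lists no laboratory tests, PK or imaging.
- **Sections 7.5 and 7.6.** Section 7.5 counts LL-BCVA as part of BCVA testing and places BCVA in the study eye at Visits 2-8. Section 7.6 uses Visits 2-9 for IOP.
- **Section 7.7.** "The following ocular images will be obtained as outlined in the visit schedule in Section 6.3", followed by a pointer to Section 1.2 as well.
- **Sections 3.2.2 and 8.1.** "Change in low luminance best corrected visual acuity (LL-BCVA" is a secondary endpoint, with no time point. Section 8.1 states "Month 2 is the first visit on treatment at which lesion area is measured" and defines ITT by a visit at or after Month 2.

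**The concern.** The list in 6.3.4 is worded as the procedures for every follow-up visit, and 6.3.3 and 6.3.5 do itemise BCVA at Day 1 and Day 150. A site could therefore take its absence between those days as deliberate.

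Several things depend on the assessments in question. Dose-limiting toxicity includes a loss of at least 15 letters within 28 days (Section 6.2). The decision to continue after the first participant at each dose is taken on 28-day data. The DSMB reviews acuity loss and laboratory data at one month (Section 9.7). Tolerability is judged partly on laboratory abnormalities (Sections 6.2 and 8.3). Section 2.3.3 says the drug has not been given intravitreally to people before. The trial is very small (9 participants in the synopsis, up to 12 in Section 8.6), and Section 8.7 says missing data will generally not be imputed, so a missed assessment cannot be made good.

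**Working it through.** No formula applies. The check counts scheduled time points, SoA columns against the lists in 6.3.1 to 6.3.5.

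| Assessment | SoA | Section 6.3 |
|---|---|---|
| BCVA, all | 9 (every column) | 4 (screening, Days 0, 1, 150) |
| BCVA, post-dose to Day 28 | 4 (Days 1, 7, 14, 28) | 1 (Day 1) |
| FAF, all | 9 | 2 (screening, Day 150) |
| FAF, post-dose | 7 | 1 (Day 150) |
| Safety labs, all | 5 (screening, Days 0, 7, 28, 150) | 2 (screening, Day 150) |
| Safety labs, post-dose to Day 28 | 2 (Days 7, 28) | 0 |
| PK | 4 (Days 0, 7, 28, 150) | 4 (Days 7, 28, 90, 150) |
| LL-BCVA | no row | 3 (screening, Days 0, 1) |

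**Does the complete ophthalmic exam fill the gap?** No. Section 7.6 defines it as external, pupil, slit-lamp and dilated fundus examination plus IOP, without an acuity test.

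**Does abridgement explain the differences?** Only in part. An abridged list can leave items out, but it cannot add one. Section 6.3.4 has a Day 90 PK sample that the SoA lacks, while 6.3.2 lacks the Day 0 PK sample that the SoA has.

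**Within Days 7-90, which laboratory visits conflict?** Only Days 7 and 28. The SoA has none at Days 14, 60 or 90 either. Section 7.9 counts five laboratory time points, which agrees with the SoA.

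**LL-BCVA after Day 1.** Section 6.3 itemises BCVA and LL-BCVA separately at screening, Day 0 and Day 1, then keeps BCVA but not LL-BCVA at Day 150. The remaining support is 7.5, which folds LL-BCVA into BCVA testing. Section 7.5 also calls screening Visit 1. On that numbering Day 0 is Visit 2, Day 90 is Visit 8 and Day 150 is Visit 9, so Visits 2-8 stop at Day 90. On the SoA numbering (Day 0 is Visit 1) Visit 8 is Day 150. The Visits 2-9 range in 7.6 fits the first numbering.

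**The Month 2 statement.** I read Month 2 as the Day 60 visit. The SoA has FAF from Day 1, so Day 60 is not the first measurement. Section 6.3.4 has no FAF at Day 60, so on that list the first is Day 150. Colour photography is first marked after dosing at Day 60 in the SoA, but lesion size is defined by FAF (synopsis, Section 3.2.2). The ITT definitions differ accordingly: the synopsis requires one efficacy measurement after dosing. A participant last seen on Day 28 with acuity and FAF recorded is in ITT under the synopsis and out under 8.1.

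**The case against.** The strongest reply is that the protocol already says where the full schedule is. Section 6.3 refers to the SoA, and the opening of Section 7 places the evaluations in the SoA. Section 7.5 has BCVA at Visits 2-8, which covers Days 1, 7, 14 and 28 on either numbering. Section 7.7 also points to Section 1.2. On this view 6.3.4 is only an incomplete summary.

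Much of that stands, and it rules out several stronger readings that a reader might reach:

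- *The acuity component of dose-limiting toxicity is not measured.* Not supported: the SoA and 7.5 both schedule it across the 28 days.
- *LL-BCVA can have no value after Day 1.* Not supported: 7.5 gives an implied route wherever BCVA is tested.
- *The lesion-size endpoint cannot be computed.* Not supported: screening and Day 150 FAF are in both lists, so change from baseline to Month 6 is available. Only the exploratory by-visit lesion analysis would be lost under 6.3.
- *Laboratory tests are missing throughout Days 7-90.* Not supported beyond Days 7 and 28.

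The reply does not remove the conflict. It leaves the PK days unexplained, and 7.7 names both sources without ranking them. The LL-BCVA route is only implicit, conflicts with the separate listing in 6.3, and is uncertain at Day 150. The Month 2 statement agrees with no schedule in the protocol.

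**Conclusion.** The protocol contains conflicting assessment schedules that should be reconciled. Size, if a site followed 6.3 alone: one post-dose BCVA within 28 days instead of four, no post-dose safety laboratory tests by Day 28 instead of two, one post-dose FAF instead of seven, and PK on Day 90 in place of Day 0. A site that follows the SoA avoids the BCVA, FAF and laboratory losses, so these are a risk in conduct and not a planned omission.

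Two parts do not depend on which list a site uses. LL-BCVA has no explicit visit after Day 1 in either schedule, and its Day 150 measurement depends on how visits are numbered. Section 8.1 rests its efficacy population on a statement that both schedules contradict, and its definition differs from the synopsis.

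The counts assume that the SoA marks were read from the correct columns; the four PK and five laboratory time points in Section 7.9 agree with that reading.

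**What to change.** - Reconcile 6.3.2 to 6.3.5 with the SoA row by row: BCVA, SD-OCT, FAF, safety laboratory tests and PK days, including Day 0.
- Use one visit numbering in 1.2, 6.3, 7.5 and 7.6.
- Give LL-BCVA its own SoA row with explicit visits that include Day 150, and repeat them in 6.3; otherwise drop it as an endpoint.
- In 7.7, name the SoA as the governing schedule for imaging.
- In 8.1, correct the Month 2 statement and the ITT definition that depends on it, so that both agree with the SoA and the synopsis.

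This is a wording amendment. The visits already take place; the cost is a few minutes of extra acuity testing at those where LL-BCVA is added.

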2.2.3 ANIMAL STUDIES

An animal study was conducted to evaluate the safety and efficiency of Fludrocortisone acetate after intravitreal injection into the vitreous cavity [30]. Surgeries were performed on the eyes of 25 New Zealand white rabbits. Fludrocortisone acetate was titrated using sterile BSS solution to the following concentrations: 4 mg/ 0.1 ml, 2 mg/ 0.1 ml, 1 mg/0.1 ml, and 400 µg/0.1 ml, which were injected intravitreal into one eye of twenty-five rabbit eyes. The control eyes received 0.1 ml of sterile BSS. All animals were examined before and after injection using indirect ophthalmoscope and slit-lamp biomicroscopy. Electroretinography (ERG) was performed on all animals prior to intravitreal injection and two weeks after injection. The animals were re-examined at this time by indirect ophthalmoscope and slit-lamp biomicroscopy and were euthanized. Their eyes were enucleated and examined with light microscopy.

Outcomes from these in vivo tests were positive for the application of intravitreal Fludrocortisone acetate. In multiple measurements, up to 40 days of observations, the slit lamp biomicroscopy and indirect ophthalmoscopy did not show any evidence of significant inflammation in the anterior or posterior segment of the eye in either the control or treatment groups. Intraocular pressure (IOP) was normal across all groups. Histological examination of retinal sections, under light microscopy, revealed that the integrity of the retinal layers appeared preserved with no evidence of toxicity or vacuolization except for one eye in the 4mg group. All aggregates of Fludrocortisone acetate disappeared by 22 +/-8 days in the 2-mg group, and 33 +/-7 days in the 4-mg group.

In ERG testing, one eye injected with 4mg/0.1ml exhibited decreases in ERG output. All other eyes had a normal ERG. These findings represent promising results for intravitreal Fludrocortisone acetate that is clinically suitable for both short-term and long-term use.

Data from the light-damage model of dry AMD in mice showed FCA delivered in Kenalog vehicle resulted in significantly less cell death, and significantly fewer macrophages that carry the IBA1 marker 7 days later. Histology shows that the animals

treated with FCA have a much thicker outer nuclear layer. Treated animals have a significantly more robust Electroretinogram A-wave (Photoreceptor function) and B-wave (inner retinal function).

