7.9 BLOOD VOLUME FOR STUDY ASSESSMENTS

Blood volume during study (up to Day 150)

Assay	Number of Time Points	Approximate Volume per Time Point (mL)	Approximate Sample Volume Over Course of Study (mL)
Pharmacokinetics	4/9	4	36
Haematology	5/9	4	36
Chemistry (Incl. HCG/LH/FSH)	5/9	8.5	76.5

Total Blood Volume for Study 148.5 mL

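### The two PK schedules conflict, and under either one the first certain post-dose sample is Day 7, so the listed Cmax and Tmax cannot describe a first-week peak and the half-life may not be estimable

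*Protocol*

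**What the plan says.** Section 3.2.2 lists the PK parameters as exposure after a single dose, "Serum maximum observed concentration", "Time to maximum measured concentration" and "Terminal elimination half-life". The synopsis lists the same four.

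The sampling days appear in two places:

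- **Section 1.2 (Schedule of Activities).** The row "Pharmacokinetic sampling" is marked at Day 0, Day 7, Day 28 and Day 150. Nothing says whether the Day 0 sample precedes or follows the injection.
- **Section 6.3.** The Day 0 list (6.3.2) contains no PK draw. For the follow-up visits, 6.3.4 says "Collect blood for PK analysis (days 7, 28 and 90 only". For Day 150, 6.3.5 says "Collect blood for PK analysis".

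Neither place has a PK sample on Day 1 or Day 14, although both visits exist.

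Section 7.9 counts 4 PK, 5 haematology and 5 chemistry time points out of 9 and ends with "Total Blood Volume for Study 148.5 mL". Section 2.3.3 repeats this as roughly 150 mL and points to Section 9.9, although the table is in 7.9.

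The only information on how long the drug persists in the eye is from rabbits (2.2.3): "All aggregates of Fludrocortisone acetate disappeared by 22 +/-8 days in the 2-mg group".

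**The concern.** A site cannot follow both schedules. The count of four PK time points in 7.9 does not settle the matter, because each schedule has four.

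The larger question is whether the samples can support the listed parameters. If the first certain post-dose sample is a week after injection, the maximum observed concentration is the largest value from Day 7 onward and its time is one of a few visit days. If serum concentration peaks within the first week, neither figure describes that peak, and any early systemic event could not be related to a concentration.

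This matters because, by 2.3.3, fludrocortisone has not previously been given intravitreally in humans, and the synopsis gives possible avoidance of systemic effects as part of the dose rationale. An analysis plan can define how PK parameters are computed, but it cannot supply samples that the protocol does not schedule.

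**Working it through.** **1. The schedules side by side**

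| Day | 0 | 1 | 7 | 14 | 28 | 60 | 90 | 150 |
|---|---|---|---|---|---|---|---|---|
| Section 1.2 | X (timing not stated) | – | X | – | X | – | – | X |
| Section 6.3 | – | – | X | – | X | – | X | X |

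Days 7, 28 and 150 are common. Day 0 is only in 1.2 and Day 90 only in 6.3. Certain post-dose samples number three under 1.2 (Days 7, 28, 150) and four under 6.3 (Days 7, 28, 90, 150). The possible values of the observed time to maximum are those days, plus Day 0 under 1.2 if that sample is taken after dosing.

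**2. What those days can show**

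The protocol gives no human release rate, serum half-life or assay limit, so this step is an illustration on assumed values. The model is one compartment with first-order release from the eye (half-life Ta) and first-order systemic elimination (half-life Te):

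- ka = ln 2 / Ta and ke = ln 2 / Te
- C(t) ∝ ka/(ka − ke) × (exp(−ke·t) − exp(−ka·t))
- Tmax = ln(ka/ke) / (ka − ke)

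Example: take the rabbit 22 days as about five release half-lives, so Ta = 22/5 = 4.4 days, with Te = 4 h. Then ka = 0.158 and ke = 4.159 per day, Tmax = 0.82 days, and C(7)/Cmax = 0.39.

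Percent of the true Cmax, each range running from Te = 4 h to Te = 24 h:

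| Assumed Ta (days) | True Tmax (days) | Day 7 | Day 28 | Day 90 | Day 150 |
|---|---|---|---|---|---|
| 1 | 0.5–1.4 | 1.3–10 | <0.0001 | ~0 | ~0 |
| 3 | 0.7–2.4 | 25–50 | 0.2–0.4 | ~0 | ~0 |
| 4.4 | 0.8–2.8 | 39–65 | 1.4–2.4 | ~0.0001 | ~0 |
| 7 | 0.9–3.3 | 56–79 | 7–10 | 0.015–0.022 | <0.0001 |
| 14 | 1.1–4.1 | 76–92 | 27–33 | 1.2–1.5 | 0.06–0.08 |
| 30 | 1.3–5.1 | 88–98 | 54–61 | 13–15 | 3.2–3.6 |

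Two things follow within this model:

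- The true Tmax is about 0.5 to 5 days in every scenario, before the first certain sample. Day 7 holds 1% to 98% of the peak, and the planned data cannot tell which case applies.
- With Ta up to about 7 days, Days 90 and 150 are at or below about 0.02% of the peak. That probably leaves Days 7 and 28 at best: two points for a line with two parameters, with no residual degree of freedom. With Ta = 30 days, Days 90 and 150 still carry 3% to 15%, and a crude half-life is possible.

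**3. Blood volume (Section 7.9)**

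- The stated total is reproduced by drawing every assay at all 9 visits: 9×4 + 9×4 + 9×8.5 = 36 + 36 + 76.5 = 148.5 mL.
- The table's own time points give 4×4 + 5×4 + 5×8.5 = 16 + 20 + 42.5 = 78.5 mL.
- The difference is 148.5 − 78.5 = 70 mL, so the stated total is 70/78.5 = 89% too high.
- With PK drawn on every day named in either schedule (0, 7, 28, 90, 150): 5×4 + 20 + 42.5 = 82.5 mL.

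**The case against.** Several points on the other side have force.

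- **The parameters are worded as observed and measured maxima.** Such values can be read off any set of samples. This stands: a reader might infer that Cmax and Tmax cannot be obtained at all, and the documents do not support that. The valid criticism is that they would not describe an earlier peak.
- **Loss of the half-life is conditional.** This stands too. A reader might infer from the rabbit data that Days 90 and 150 will be blank. Those data record when visible aggregates cleared from rabbit eyes after preparation in BSS, not serum concentrations. The human product uses a different diluent (5.2.2.1), and human vitreous is put at about 2.7 times the rabbit volume (2.3.2).
- **Section 6.3 calls itself condensed and refers to 1.2 for detail.** Its Day 0 list also leaves out laboratory draws, OCT and FAF that 1.2 requires, so the missing Day 0 PK draw may be mere abbreviation. That does not explain Day 90, where 6.3.4 positively names a day that 1.2 leaves empty and limits sampling to the days it names.
- **PK drives no safety decision.** It is not in the dose-limiting toxicity definition, the escalation rule or the named DSMB criteria. Vital signs are taken at every visit, and sodium and potassium on Days 7, 28 and 150. This limits the consequence. A reader might infer that the trial would wrongly report negligible systemic exposure, but the protocol plans no such claim.

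**Conclusion.** The point holds in this form. The two PK schedules disagree on Day 0 and Day 90, and the Day 0 timing is unstated. These are facts of the text and rest on no assumption.

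Under either schedule the first certain post-dose sample is Day 7 and the next Day 28, so the observed maximum and its time cannot characterise a first-week peak and may understate early exposure. By how much is unknown: the 1% to 98% range comes from an assumed first-order model with release half-lives of 1 to 30 days and systemic half-lives of 4 and 24 hours. The documents do not establish that the human peak does fall in the first week.

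The terminal half-life is doubtful rather than lost. It is unlikely to be estimable with release half-lives up to about one week and crudely estimable if release takes several weeks. The assay limit, also not given, would decide the cases in between.

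The blood total is a separate, minor arithmetic error of 70 mL. It overstates the burden on participants and conceals no risk.

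**What to change.** 1. Use one PK schedule in 1.2, 6.3 and 7.9, and state whether the Day 0 sample is taken before or after dosing.
2. Add 4 mL PK draws at the existing Day 1 and Day 14 visits. The late samples need not be dropped, since they are what would make a half-life estimable if release is slow. A draw at the 15-minute post-injection check would not replace Day 1: in every scenario above it precedes the peak.
3. If no draws are added, replace Cmax, Tmax and half-life in the synopsis and 3.2.2 with the observed concentration and the number of participants with a quantifiable value at each scheduled visit.
4. Correct 7.9 to 78.5 mL (82.5 mL if all five currently named PK days are kept), plus 4 mL per added PK draw. With both added draws this is 78.5 + 8 = 86.5 mL, or 82.5 + 8 = 90.5 mL. Check the 8.5 mL chemistry volume as well: it includes hormone tests that 7.3 places at screening only. Correct the approximate 150 mL and the section reference in 2.3.3.

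The cost is an amendment and, with item 2, up to 8 mL more blood and two more assays per participant. Even then the total stays well below the 148.5 mL already declared. Item 3 needs no extra blood.
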